### **9.2 Protocol deviation**

Deviations from the protocol should not occur. If deviations occur, the Investigator must inform B. Braun or its designee and the site's clinical research coordinator. The implications of the deviation will be reviewed and discussed.

Any deviation must be documented, including a description of the deviation, why the deviation occurred, the date of occurrence, the action taken, and the impact, if any, to the subject, clinician and/or the study.

Major Deviation Reports should be completed and forwarded to B. Braun or its designee no later than 5 working days after becoming aware of the deviation.

## 10 STUDY PROCEDURES

Table 2 outlines the timing of assessments to be performed throughout the study. See Section 6 for additional details of study procedures.

**Table 2:** Schedule of Events

Procedures	Stage of the study				
	Pre- Study	1 - Baseline	2 - Intervention and Skill Assessments	3 - Run-in	4 - Post-Interventional
Registered Nursesa	RN's	Study RN's	Study RN's	Study RN's	Study RN's
Required Site Specific Training (ie, GCP, consent process, etc)	X				
B. Braun Protocol Training	X				
Demographics		X	X b		
Standard PIVC insertion		X			
B. Braun Education and Peripheral Advantage Product Training			X		
PIVC Insertion Confidence Assessment and PIVC Knowledge Assessment			X c		X c
B. Braun Peripheral Advantage Product Insertion				X	X
Subjects					
Demographics		X			X
Informed Consent		X			X
Inclusion, Exclusion Criteria		X			X
Daily catheter monitoring		X			X
Adverse Events	--continuous--				

a All RN's may participate in Stages 1 and 2. However, only B. Braun Peripheral Advantage-trained Study RN's will participate in Stages 3 and 4.

b Demographic information to be obtained only if a new Study RN enters the study in Stage 2.

c To be performed before and after the Intervention (Stage 2) and again at the completion of the study (Stage 4).

The Investigator or designee will explain the nature of the study, the study procedures, and the potential risks to each patient. Before any study-related procedures occur, the patient must voluntarily sign the ICF.

There is no required routine collection of vital signs, physical examinations (other than the catheter site) or clinical laboratory evaluations. Safety assessments will comprise the collection, review and documentation of AEs, Serious Adverse Events (SAEs) and Adverse Device Events (ADEs).

## 11 ADVERSE EVENTS AND SERIOUS ADVERSE EVENTS

### 11.1 Adverse Events

Study safety will be evaluated by assessment of AEs.

The Study RNs in this study are subjected to minimal health risk from the use of the devices and are anticipated to be experienced users of PIVC devices. The subjects enrolled in this study may be exposed to the standard health risks associated with PIVC insertion. All events

related to both the standard-of-care products used in the hospital and the B. Braun PA and any required procedures will be evaluated for determination as AEs and documented on the eCRFs.

An AE is any untoward medical occurrence, unintended disease or injury or any untoward clinical signs (including an abnormal laboratory finding) in subjects, users or other persons, whether or not related to the investigational device. AEs may include, but are not limited to, premature device removal, minor and major complications, infection, thrombophlebitis, accidental needlestick injuries, and device failures (i.e., disconnection, twisted port hub, leakage, or failure of safety feature). AE collection for each subject will begin after the ICF is signed and will continue until the completion of all study procedures or until the subject withdraws consent or is withdrawn from the study.

AEs will be reported by the Investigator and the Sponsor will use the reported AE term to determine the MedDRA system organ class and preferred term. The investigator will also report the AE severity (mild, moderate, severe) and relationship of the AE to either the standard-of-care products used in the hospital or the B. Braun PA.

No exposure hazard is expected. The investigational devices were manufactured according to Good Manufacturing Practices (GMPs).

Specific guidelines for classifying AEs by intensity are provided in [Table 3](#).

**Table 3: Classification of Adverse Events by Severity**

Mild: An event that is easily tolerated by the patient, causing minimal discomfort and not interfering with everyday activities.
Moderate: An event that is sufficiently discomforting to interfere with normal everyday activities.
Severe: An event that prevents normal everyday activities.

When changes in the severity of an AE occur more frequently than once a day, the maximum severity for the event should be noted. If the severity category changes over a number of days, then those changes should be recorded separately (with distinct onset dates).

An Adverse Device Effect (ADE) is an AE determined to be related to the use of the investigational device.

Specific guidelines for classifying AEs by relationship are provided below:

Definite – The adverse event is clearly related to the study device: the event has a temporal relationship to the study device, follows a known pattern of response, or is otherwise logically related to the study device, and no alternative cause is present.

Probable – The adverse event is likely related to the study device: the event has a temporal relationship to the study device, follows a known or suspected pattern of response, or is otherwise logically related to the study device, but an alternative cause may be present.

Possible – The adverse event is unlikely related to the study device: the event does not follow a clear temporal relationship to the study device or does not follow a

known pattern of response, or is otherwise possibly to be due to the subject's clinical state or other modes of therapy.

In some cases, the adverse event may not be adequately assessed because information is insufficient or contradictory and/or the data cannot be verified or supplemented. Maximum effort will be made to define and categorize the event and avoid these situations. If relatedness remains uncertain, then classify the event as "possible".

Unlikely – The adverse event can be reasonably explained by another cause and/or the relationship with the use of the device seems not relevant, but additional information may be obtained.

Not Related – The adverse event is clearly not related to the study device: the event has no temporal or other relationship to the administration of the investigational device follows no known or suspected pattern of response, and an alternative cause is present.

## **11.2 Serious Adverse Events and Serious Adverse Device Effects**

An AE is considered "serious" if in the view of either the Investigator or Sponsor, it meets 1 or more of the following criteria:

- led to death,
- led to serious deterioration in the health of the subject, that either resulted in
- a life-threatening illness or injury, or
- a permanent impairment of a body structure or a body function, or
- in-patient or prolonged hospitalization, or
- medical or surgical intervention to prevent life-threatening illness or injury or permanent impairment to a body structure or a body function, or
- led to fetal distress, fetal death or a congenital abnormality or birth defect

A serious ADE is an Adverse Device Effect that has resulted in any of the consequences characteristic of an SAE.

## **11.3 Event Reporting**

All events related to both the standard-of-care products used in the hospital and the B. Braun Peripheral Advantage Program devices and any required procedures will be evaluated by the Investigator for determination as AEs, SAEs, ADEs and documented on the electronic case report form (eCRF). AE collection for each subject will begin after the informed consent form is signed and will continue until the completion of all study procedures or subject withdrawal from the study.

All SAEs will be followed until the Investigator and Sponsor agree the event is satisfactorily resolved (i.e., resolved, stabilized or returned to baseline). Preliminary reports of SAEs must be followed by detailed descriptions later on, including clear and anonymized photocopies of hospital case reports, consultant reports, autopsy reports, and other documents when

requested and applicable. SAE reports must be made whether or not the Investigator considers the event to be related to the study device.

An SAE occurring during the study must be reported to the Sponsor or designee. Any such SAE due to any cause, whether or not related to the study devices, must be reported within 24 hours of occurrence or when the Investigator becomes aware of the event.

Appropriate remedial measures should be taken to treat the SAE, and the response should be recorded. Clinical, laboratory, and diagnostic measures should be employed as needed in order to determine the etiology of the problem. All SAEs will be followed until the Investigator and Sponsor agree the event is satisfactorily resolved. The Sponsor will report SAEs to the FDA as required.

In the event of an adverse device effect or device malfunction, form FDA 3500 MedWatch must be completed. E-mail Form FDA 3500 MedWatch and any supporting documentation as instructed below within 24 hours of becoming aware of the event.

- a. During Stage 1 of the protocol, notification shall be made by email to [contact] and [contact].
- b. During Stage 4 of the protocol, notification shall be made to the Sponsor's Medical Affairs Department either by phone call: [contact] or email to [contact].

Unanticipated Serious Adverse Device Effects (USADEs) are serious adverse device effects which by nature, incidence, severity or outcome have not been identified in the current version of the risk analysis report. SAEs which are attributed by the Investigator to the patient's underlying medical condition and unrelated to the study device will not be reported as USADEs. The Sponsor is responsible for expedited reporting of USADEs to the FDA.

The Investigator is responsible for notifying the Institutional Review Board (IRB).

#### **11.4 Reporting responsibility and procedures**

A needlestick-related event reportable under 21 CFR Part 803 includes any death, serious injury, or malfunction for either the standard-of-care products used in the hospital or the B. Braun PA products as detailed below:

A death report should be submitted by a user facility, importer, and manufacturer if the device may have caused or contributed to the death of an individual.

A serious injury report (Form FDA 3500 MedWatch) should be submitted by a user facility, importer, and manufacturer if the device resulted in an injury to an individual and the injury was life-threatening, resulted in permanent impairment of a body function or permanent damage to a body structure, or necessitated medical or surgical intervention to preclude permanent impairment of a body function or permanent damage to a body structure.

A device malfunction report (Form FDA 3500 MedWatch) should be submitted by an importer and manufacturer if the device failed to perform as intended and would be likely to cause or contribute to a death or serious injury if the needlestick event reoccurred. B. Braun should also be notified of SAEs and of any follow-up information in writing using the Form FDA 3500 MedWatch, as is practical, and depending on local regulations ([Needlesticks, 2002](#)).

## 12 STATISTICAL ANALYSIS

The statistical evaluation will be performed using the Statistical Analysis Software (SAS®) Version 9.2 or higher (SAS Institute, Cary, NC). All data will be summarized using descriptive statistics, and where necessary, data will also be listed either by subject or by event, as appropriate. For continuous variables, data will be summarized with the number of subjects (N), mean, standard deviation (SD), median, minimum, and maximum. For categorical variables, data will be tabulated with the number and proportion of subjects for each category. Where appropriate, 95% two-sided confidence intervals may be presented. If the observed data are found not to follow a normal distribution, appropriate non-parametric methods may be employed. Two interim analyses are planned.

All hypothesis tests will be two-sided and performed at the alpha=0.05 level. No adjustments to the alpha level will be made for the number of significance tests performed.

Data obtained from all subjects who enroll in any Stage(s) of the study and data obtained from the RN's participating in the study will be included in analysis of safety and the study endpoints.

Additional data driven subgroup analyses may be performed. Additional details on the statistical analyses will be describe in the separate Statistical Analyses Plan (SAP).

### 12.1 Statistical Analyses for Primary Endpoint

#### Incidence of Complications Associated with PIVC Use

The statistical analysis will compare the rate/percentage of complications between B. Braun PA and hospital's current standard-of-care PIVC utilizing a binomial test (such as Fisher's Exact Test). The source data are the evaluations of catheter placements, i.e., were there any complications? (Yes/No), was there removal of the catheter due to complications? (Yes/No) (e.g., due to phlebitis, occlusion, infection, dislodgement, infiltration, etc.).

### 12.2 Statistical Analyses for Secondary Endpoints

Standard statistical methods will be utilized in this study to analyze all data. Secondary endpoints that measure rates (e.g., first stick success) will be tested for significance using a binomial test (such as Fisher's exact test). Continuous endpoints will be tested for significance using standard parametric tests (such as Student's t-test), or non-parametric equivalent (such as Wilcoxon signed rank test) if parametric methods are found to be inappropriate.

Indwell Times: The source data are the indwell times measured for all catheters (e.g., catheter withdrawn due to complications, end of medical treatment, routine catheter change, end of treatment or voluntary withdrawal of subject from study). The indwell time is calculated from the time of catheter insertion until the time of catheter removal for any reason. In the event the subject or his/her LAR withdraws consent or is withdrawn by the PI, for any reason, and the catheter is still in place, the date and time of withdrawal will be used as a surrogate for the date and time of removal.

A survival analysis will be performed to further understand the difference in indwell times. A catheter will be considered to have been a failure/event if it is removed due to any

complication or failure of the unit. It will be considered censored/non-event if it is removed as it is no longer needed, i.e., the condition improves or the subject is discharged from the hospital.

### **12.3 Safety Analyses**

Adverse events will be summarized as an overall incidence of at least one event, incidence within system organ class only, and incidence by system organ class and preferred term. Events may include, but are not limited to: minor and major complications, infection, thrombus, phlebitis, accidental needle sticks, and device failures (i.e., disconnection, twisted port hub, leakage, and failure of the safety feature). [Section 11](#) of this protocol details AE definitions and relationship classifications.

A Statistical Analysis Plan (SAP) will be prepared after the protocol and eCRF are approved. This document will provide further details regarding the definition of analysis variables and analysis methodology to address all study objectives. The SAP will serve as a complement to the protocol and supersedes it in the case of any differences.

### **12.4 Determination of Sample Size**

Based on initial study design assumptions, at least 316 successful PIVC insertions are necessary to complete Stage 1 and at least 316 successful PICV insertions are necessary to complete Stage 4 in order to detect a statistically significant difference between the current standard-of-care and B. Braun PA at 90% power and two-sided confidence level of 5.0%. The estimated complication rate in Stage 1 is 50% and the estimated complication rate in Stage 4 is 35%. ([Helm, 2015](#))

Two interim analyses are planned, solely for the purpose of sample size re-estimation. Using the method of Pocock & Mehta, the sample size can be either held constant or increased – it cannot be reduced based on the results of the re-estimation.

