#### **Interim Data Analysis Stage 1**

Upon successful completion of approximately 70% of the originally planned PICV placements in Stage 1, an interim analysis of the primary endpoint on raw (uncleaned) data will be performed. The observed complication rate in Stage 1, utilizing actual data collected in the study up to this point, will be compared to the originally estimated complication rate of 50%. If the observed complication rate is statistically significantly greater than 50%, the sample size will not be modified, and Stage 1 enrollment will continue to the original sample size of at least 316 successful PIVC insertions. If the observed complication rate is not statistically significantly greater than 50%, the sample size may be re-estimated with the assumed Stage 1 complication rate equal to the observed interim analysis complication rate, with other assumptions held constant.

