#### **Interim Data Analysis Stage 4**

The final sample size in Stage 1 (based on the results of the sample size re-estimation in Stage 1) will be used as the initial sample size for Stage 4. Upon successful completion of approximately 50% of the initial sample size in Stage 4 (which is determined at the interim analysis in Stage 1), another interim analysis on raw (uncleaned) data for the complications will be performed. This sample size re-estimation will follow the method of Mehta and

Pocock to calculate the conditional power of the study to conclude that the complication rate in Stage 4 is lower than the complication rate in Stage 1, given the observed complication rates at the interim analysis. The conditional power (CP) will be categorized into one of the three following zones:

- Favorable:  $CP \geq 90\%$
- Promising:  $41\% \leq CP < 90\%$
- Unfavorable:  $CP < 41\%$

In the event the conditional power is found to be in the Favorable or Unfavorable zone, the study will continue to the originally planned sample size in Stage 4 (i.e., final sample size in Stage 1). In the event the conditional power is in the Promising zone, the total study sample size may be increased to the required sample size to achieve conditional power of 90% at the completion of the study. Note that only the sample size in Stage 4 can be increased at this time, as the data collection in Stage 1 has been completed.

**Registered nurses:** Only RNs from the hospital's ED or medical surgical departments/unit will participate. Registered nurses can be on any shift and will not be required to have a minimum level of clinical experience. There is no minimum number of RNs required.

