**Subjects:** Subjects or their LAR will be consented before participating in Stage 1 and/or Stage 4 and may participate in either, or both, of those stages. Subjects consented for Stage 1 may participate as patients in Stage 3 (Run-In). If the PIVC was removed for a complication, then the subject may not continue or re-enter into the study and he/she is considered a Study Completer. If the PIVC was removed as a result of treatment completion (i.e., subject no longer requires a PIVC) he/she will be considered a Study Completer. In addition, if he/she was subsequently discharged from the facility, then he/she may re-enter the study in the same or different Stage if a re-admission for any reason is required. Subjects who participate in more than one stage, or more than once in a single stage, will be considered independent for all analyses.

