## 6.2. Description of Study Hypotheses

The primary hypothesis is that the rate or percentage of complications in the patients in Stage 4 utilizing the B. Braun Peripheral Advantage Program will be lower than the rate in the baseline at Stage 1 utilizing the site's current standard of care with regards to PIVC insertion technique used and Institution's PIVC type.

The study's null and alternative hypotheses are as follows:

$$H_0: P_{\text{Stage 4}} \geq P_{\text{Stage 1}}$$

$$H_a: P_{\text{Stage 4}} < P_{\text{Stage 1}}$$

where  $P_{\text{Stage 1}}$  and  $P_{\text{Stage 4}}$  represent the rate or percentage of complications in Stage 1 and Stage 4, respectively.

**Decision Criterion:** The null hypothesis will be rejected and the alternative hypothesis will be concluded if the upper confidence limit for the rate difference, i.e.  $P_{\text{Stage 4}} - P_{\text{Stage 1}}$ , of a 1-sided 95% confidence limit (normal approximation) is less than zero.

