## 9. STATISTICAL METHODS

### 9.1. Determination of Sample Size

Based on initial study design assumptions, at least 316 successful PIVC insertions are necessary to complete Stage 1 and at least 316 successful PIVC insertions are necessary to complete

Stage 4 in order to detect a statistically significant difference between the current standard-of-care products and B. Braun PA at 90% power and two-sided confidence level of 5.0%. The estimated complication rate in Stage 1 is 50% and the estimated complication rate in Stage 4 is 35% (Helm, 2015).

Two (2) interim analyses of raw data are planned solely for the purpose of sample size re-estimation. Using the method of Pocock & Mehta, the sample size can be either held constant or increased – it cannot be reduced based on the results of the re-estimation.

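### The 316 placements per stage do not follow from the stated sizing inputs, which need about 227 (242 with Fisher's exact test); 316 gives about 97% power, not 90%

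*Protocol*

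**What the plan says.** Protocol 12.4 states that "at least 316 successful PIVC insertions are necessary to complete Stage 1" and gives the same minimum for Stage 4, 632 in total. The basis is given as "at 90% power and two-sided confidence level of 5.0%. The estimated complication rate in Stage 1 is 50" per cent, with 35% expected in Stage 4. SAP 9.1 repeats the rates, the number and the basis: "at 90% power and two-sided confidence level of 5.0". Neither document names a formula or software.

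The surrounding text bears on how 316 might have been reached:

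- **Re-estimation.** Protocol 12.4 and SAP 9.1 let two interim looks raise the sample size, but "it cannot be reduced based on the results of the re-estimation". At the Stage 1 look the size may be recalculated with the Stage 1 rate set "equal to the observed interim analysis complication rate, with other assumptions held constant".
- **Independence.** For people who take part more than once, Protocol 12.4 (Subjects) says that they "will be considered independent for all analyses".
- **Losses.** The target counts successful placements only. Protocol 13.2 handles subjects who withdraw with the catheter still in place as completers.
- **Alpha.** Protocol 12 makes all tests two-sided at 0.05 with no adjustment for the number of tests. SAP 6.2 instead rejects the null hypothesis if the upper bound of a "1-sided 95% confidence limit (normal approximation) is less than zero", and SAP 9.2.10 makes every test one-sided at 0.05.
- **Status.** SAP 10 records that the study was terminated for recruitment futility before Stage 2, so no Stage 4 analysis will be done.

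**The concern.** A sample size statement should let a reader get from the inputs to the number. Here every input needed for a comparison of two proportions is given, and the number they produce is well below the one stated. As written, 316 is called necessary for 90% power, and on the stated inputs it is not.

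The main consequence is that the quoted power is not the power of the design. A second is that 316 is the starting point for the Stage 1 re-estimation. That step keeps the other assumptions fixed, so it can be repeated only if the reader knows which calculation they belong to.

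**Working it through.** **Inputs.** p1 = 0.50 (Stage 1), p2 = 0.35 (Stage 4), difference d = 0.15, two-sided alpha 0.05, power 0.90, equal stages (Protocol 12.4, SAP 9.1). I read the two-sided 5% confidence level as the significance level. The test is a binomial test, with Fisher's exact test as the example (Protocol 12.1).

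**Attempt to reproduce 316.**

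Pooled normal formula, with mean rate (0.50 + 0.35)/2 = 0.425:

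- n = [1.960 × √(2 × 0.425 × 0.575) + 1.2816 × √(0.25 + 0.2275)]² / 0.15²
- = [1.960 × 0.6991 + 1.2816 × 0.6910]² / 0.0225 = 226.2, so **227**.

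Other methods on the same inputs:

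| Method | n per stage |
|---|---|
| Unpooled normal | 223 |
| Arcsine | 227 |
| Continuity-corrected: (226.2/4) × [1 + √(1 + 4/(226.2 × 0.15))]² = 239.3 | 240 |
| Two-sided Fisher, full enumeration (power 0.8994 at 241, 0.9009 at 242) | 242 |
| Stated in the plan | 316 |

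The figure is not reproduced. The excess is 316 − 227 = 89 (39%), or 316 − 242 = 74 (31%) against Fisher. Using 95% power instead gives 280 (293 continuity-corrected), so a slip to that power does not explain it. Reading 316 as a two-stage total fails too, because the documents give 632 in total.

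**Power at 316 per stage, independent placements.**

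- Normal approximation: z = (0.15 × √316 − 1.960 × 0.6991)/0.6910 = (2.666 − 1.370)/0.691 = 1.876, so power is **97.0%**.
- Two-sided Fisher, full enumeration: **96.3%**.

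**Is there a stated allowance?** A loss allowance would have to be 1 − 227/316 = 28%, or 1 − 242/316 = 23% on the Fisher basis. None is given, and the target already counts only successful placements. No design effect is given for nurse, hospital or repeat participation. Alpha is not adjusted, and the interim looks are described as being for re-estimation only.

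**What this does to the Stage 1 re-estimation.** Take an observed Stage 1 rate of 48%, with Stage 4 at 35%, two-sided 5% and 90% power:

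- Pooled: 299.8, so 300, below the floor of 316.
- Continuity-corrected: 315.0005, so about 316, at the floor.
- Two-sided Fisher: power 0.8990 at 316 and 0.9000 at 317, so 317, one above the floor.

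Near 48% the answer therefore turns on the formula, which the plan does not name.

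**Secondary: sidedness.** Under the one-sided 5% rule of SAP 6.2 and 9.2.10, the pooled formula with 1.645 in place of 1.960 gives 184.1, so 185 per stage. Power at 316 is then Φ[(2.666 − 1.645 × 0.6991)/0.6910] = Φ(2.195) = 98.6%.

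**The case against.** The strongest reply is that 316 is a stated minimum which meets the 90% goal with room to spare, so nothing is endangered. That stands as far as it goes: the error is on the safe side. It does not make the statement correct, because 316 is presented as what 90% power requires.

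A second reply is that 316 may contain a deliberate margin, for clustering or unusable placements for example. This cannot be excluded. A reader might infer from the mismatch that the sponsor miscalculated. The documents do not support that; they show only that the derivation is missing.

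A third reply concerns the re-estimation. A reader might infer that it should carry whatever hidden margin lies in 316, and so would give much larger targets than the stated inputs do. That requires bases that appear nowhere in the documents, and the plan says only that the size may be re-estimated. What stands is narrower: the formula is not named, and close to the floor this changes the answer by a few placements.

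A reader might also link the larger target to the recruitment failure. SAP 10 reports the failure, but nothing there attributes it to the target.

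Finally, the sidedness conflict is a separate matter that neither causes nor explains 316. That is right. It belongs here only because the power to be quoted depends on which rule is kept.

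**Conclusion.** The point holds and is minor. On the plan's own inputs, 90% power needs 227 placements per stage (240 continuity-corrected, 242 Fisher). The stated 316 gives about 97% (96% Fisher), and nothing stated closes the gap. The power figures assume independent placements; with correlation within nurse, hospital or patient, the power of 316 would be lower by an amount the documents do not allow one to calculate.

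The discrepancy adds no bias and does not inflate the type I error. Its practical weight is small, since the Stage 1 against Stage 4 comparison will not be made. The defect is an undocumented derivation and a misquoted power, not a demonstrated miscalculation and not a flaw that endangers a conclusion.

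The secondary point also holds. SAP 9.1 sizes two-sided at 5%, in line with the two-sided testing in Protocol 12, while SAP 6.2 and 9.2.10 decide one-sided at 5%. Under either rule the power of 316 is not 90%.

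**What to change.** Keep 316. In Protocol 12.4 and SAP 9.1, do one of two things:

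1. State the assumption that produced 316 (loss, clustering, higher power or other).
2. Restate the power as about 97% (96% with Fisher's exact test) for 50% against 35% at two-sided 5%, conditional on independent placements.

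In either case, name the formula or exact test used, so that the Stage 1 re-estimation in Protocol 12.4 and SAP 9.1.1 can be repeated. Reconcile the two-sided sizing in SAP 9.1 with the one-sided rule in SAP 6.2 and 9.2.10, and quote the power of 316 under the rule that is kept. As the study has ended, carry the corrected statement into the study report.

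The cost is a few sentences. The number of placements does not change and no further patients are needed.
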